| EASO | 
European Association for the Study of Obesity
 
EASO is a federation of professional membership associations from 34 European countries. It is the voice of the European obesity community, representing scientists, health care practitioners, physicians, public health experts and patients. EASO is in official relations with the World Health Organisation (WHO) Regional Office for Europe and is a founding member of the EU Platform on Diet, Physical Activity and Health.
 |
| SWiM | 
Supporting Weight Management during COVID-19
 
A web-based supported self-help intervention that aims to support adults with overweight and obesity to prevent weight gain by helping them to manage their eating behaviours, be more physically active and protect their emotional wellbeing.
 |
| - SWiM Sessions | Weekly modules delivering educational material, reflective exercises and behavioural experiments based on Acceptance and Commitment Therapy (ACT) and habit theory. |
| - SWiM Coach | A trained member of the SWiM team providing telephone and email-based support to intervention participants. |
| - SWiM Practice | Reflective exercises and behavioural experiments assigned at the end of SWiM Sessions for participants to complete between sessions. |
| - SWiM Aids | A feature of the SWiM platform that collates the core exercises and concepts from each SWiM Session, providing the participants with easy access to the core intervention components. |

Figure 1: TRIAL FLOW CHART

1. BACKGROUND

The social distancing and isolation measures imposed during the COVID-19 pandemic beginning March 2020, including the closure of community weight management programmes and services, mean that adults with overweight and obesity in the UK are at increasing vulnerability to weight gain, and associated negative impacts on physical health and mental wellbeing. Usual habits and routines are disrupted, stress and anxiety are likely to be high, usual coping mechanisms may be limited, and people are likely to respond by developing unhealthy habits such as comfort eating and sedentary behaviour and may experience increased low mood resulting from this. We have previously shown that preventing weight gain can reduce diabetes incidence amongst people with type 2 diabetes, even among people who already have overweight or obesity.(1) Other studies show that annual weight gain can typically be attributed to discrete periods of time (e.g. holidays) and that this weight gain is typically not compensated for.(2,3) Thus, weight gain during social distancing could have a significant impact on the health and wellbeing of people with overweight and obesity.

There is good evidence that interventions based on acceptance and commitment therapy (ACT) are effective for weight management and may improve mental wellbeing and psychological determinants of weight control.(4) However, acceptance-based programmes are usually psychologist-led and the cost and scarcity of psychologists specialising in obesity mean it is not possible to support everyone who would benefit from this type of intervention. It is possible to deliver self-help versions of acceptance-based programmes.(5) However, there is currently insufficient evidence on mode of delivery or cost-effectiveness to recommend scalable implementation of self-help versions of acceptance-based interventions, particularly in the context of weight management.(4)

We have developed a supported self-help intervention (SWiM; Supporting Weight Management during COVID 19) that aims to help adults with overweight and obesity to manage their weight and eating behaviour, be more physically active, and protect their emotional wellbeing. This intervention is adapted from the SWiM programme, which was originally developed to help people to maintain weight after weight loss. The adaptations speak specifically to the restrictions associated with COVID 19, including outside access, social distancing, and isolation. The 12-week intervention is based on ACT, targets known psychological determinants of weight management and is delivered via an online platform with remote support from a guide or coach. The current study compares the effectiveness of SWiM with standard written materials giving advice on diet, physical activity and mental health during the COVID-19 pandemic.

The COVID19 crisis represents a unique situation of unknown duration, but some form of social distancing is likely to last for many months and could reoccur. If the SWiM intervention proves to be effective it could be rolled out on a larger scale to support people through the current crisis. Findings may also be generalisable to other situations involving high levels of stress, reduced access to resources, and/or low levels of mobility. Qualitative interviews with participants will give insight into the extent to which findings from this study are context dependent and give insight into how the intervention could be adapted for other contexts.

2. AIMS AND OBJECTIVES

2.1 Aim

To evaluate the effect of the SWiM intervention on weight, eating behaviour, physical activity and wellbeing compared to current standard advice for people with overweight and obesity. Primary Objective

To evaluate the effect of SWiM on weight at 4 months and 12 months follow-up, compared to standard advice on diet, physical activity and mood.

2.2 Secondary Objectives

To evaluate the effect of SWiM on eating behaviour, physical activity and psychological wellbeing compared to standard advice.

To evaluate the cost-effectiveness of the SWiM intervention compared to standard advice.

To understand the experience of participants and the extent to which the programme meets their needs.

To explore potential causal mechanisms, and contextual factors that may be associated with variations in outcome.

3. STUDY DESIGN

This is a pragmatic, randomised, single-blind, parallel group, two-arm trial. Participants will be randomised to either the SWiM intervention or to a standard advice wait list control using a computer-generated sequence with 1:1 allocation stratified by sex and BMI classification.

Participants will complete outcome assessments online at baseline, at 4 months and at 12 months follow-up.

4. PARTICIPANTS

Participants (N=360) will be adults with overweight or obesity (Age ≥ 18 years; BMI ≥ 25 kg/m²) who have a good understanding of written English (materials are not suitable for non-English language speakers), are willing to be randomised to either intervention and to complete outcome assessments online, and who own a set of scales that they can weigh themselves with during the study. Participants will be excluded from taking part if they have had bariatric surgery in the last 2 years.

4.1 Recruitment

Participants will be recruited online through obesity and weight management organisations, volunteer databases and social media. Recruitment adverts have been reviewed by patient and public involvement representatives to ensure sensitivity. Adverts and email invitations will include a link to a secure web form which will be used to provide participant information, confirm eligibility, and obtain informed consent. Once informed consent is given, baseline data will be collected.

4.2 Randomisation

Once baseline data have been collected, eligible participants will be allocated to one of the two intervention arms in a 1:1 allocation using block randomisation (block size 6) stratified by BMI classification (25-30, 30-40, 40+) and sex (male, female). The randomisation sequence will be computer-generated by the trial statistician and incorporated into the trial database by the data manager. The sequence will be unknown to all other personnel, including study coordinators, outcome assessors and investigators.

Randomised allocation will be revealed to the participant by phone or email, which will provide detail of the allocated intervention. If they have been allocated to SWiM, they will receive a web link to access the website with instructions for getting started. If allocated to standard advice waitlist control, they will be emailed a PDF of the European Association for the Study of Obesity (EASO) guidance on diet, physical activity and mood during the COVID 19 pandemic.(6)

5. PLANNED INTERVENTION AND CONTROL

5.1 Supporting Weight Management during the COVID-19 pandemic (SWiM) programme

SWiM is a supported self-help programme that uses acceptance-based strategies to support adults with overweight and obesity to manage their weight and eating behaviour, be more physically active, and protect their emotional wellbeing. The intervention includes access to an online web platform with 12 modules (SWiM sessions) consisting of psychoeducational content, reflective exercises, and behavioural experiments. Content is described in Table 1. SWiM is intended to be a 12 week intervention, with 1 session completed per week. Participants are encouraged to weigh themselves weekly and to record their weight at the start of each session. Between sessions, participants are asked to complete more reflective exercises and behavioural experiments known as 'SWiM Practice'. Automated email reminders are sent to participants to remind them to log in and complete sessions each week. After the participant has completed the week 4 session, they will receive a telephone call from their SWiM Coach. This will be a 20 minute call to check in and see how the participant is getting on with the intervention and to ensure they understand the content. A

tailored email will also be sent at week 10. At the end of the study, participants will then receive the same standard advice materials as the control group.

| Session | Content |
|--|---|
| Welcome to SWiM | What is SWiM? |
| | Let's take a tour around SWiM! |
| | Meet the SWiM Team |
| Session 1: Eating Well During Lockdown | 1.0 Tracking Your Progress |
| | 1.1 Eating Well During The Lockdown |
| | 1.2 Alcohol and COVID19 |
| | 1.3 SWiM Practice: Planning Your Meals |
| Session 2: Staying Active During Lockdown | 2.0 Checking in |
| | 2.1 Physical Activity and COVID19 |
| | 2.2 Physical Activity Recommendations |
| | 2.2 Tips for Staying Active |
| | 2.3 SWiM Practice: Your Physical Activity Plan |
| Session 3: Planning and Goal-Setting | 3.0 Checking in |
| | 3.1 Your Weight Maintenance Plan |
| | 3.2 SMART Goals and Plans |
| | 3.3 SWiM Practice: Goal Setting |
| Session 4: Control and Acceptance | 4.0 Checking in |
| | 4.1 Control and Acceptance |
| | 4.2 What Matters to You? |
| | 4.3 SWiM Practice: Values, Goals and Actions |
| Session 5: Being Willing | 5.0 Checking in |
| | 5.1 Values and Goals |
| | 5.2 Being Willing |
| | 5.3 SWiM Practice: 'Even If...' Thoughts |
| Session 6: Overcoming Obstacles | 6.0 Checking in |
| | 6.1 Identifying Your Obstacles |
| | 6.2 Planning for Obstacles |
| | 6.3 How to Deal with a Lapse |
| | 6.4 SWiM Practice: Being BOLD |
| Session 7: Emotional Eating | 7.0 Checking in |
| | 7.1 What is Emotional Eating? |
| | 7.2 Breaking the Cycle |
| | 7.3 SWiM Practice: Emotional Responses Diary |
| Session 8: Stress Management | 8.0 Checking in |
| | 8.1 Stress and Weight Gain |
| | 8.2 Control What You Can, Accept What You Can't |
| | 8.3 Defusion: Unplugging the Sink |
| | 8.4 Mindful Breathing |
| | 8.5 How to get a good night's sleep |
| | 8.6 SWiM Practice: Practising Defusion |
| Session 9: Urges and Cravings | 9.0 Checking in |
| | 9.1 We All Have Urges and Cravings |
| | 9.2 Recapping Defusion |
| | 9.3 Urge Surfing |

| | |
|--|---|
| | 9.4 SWiM Practice: Learning to Surf |
| Session 10: Habits and Being Flexible | 10.0 Checking in |
| | 10.1 Forming Helpful Habits |
| | 10.2 Breaking Unhelpful Habits |
| | 10.3 Being Flexible |
| | 10.4 SWiM Practice: Breaking Unhelpful Habits |
| Session 11: Weight Stigma and Self-Acceptance | 11.0 Checking in |
| | 11.1 The Impact of Weight Stigma |
| | 11.2 How to Deal with Weight Stigma |
| | 11.3 Self-Acceptance |
| | 11.4 SWiM Practice: Practicing Self-Acceptance |
| Session 12: Friends and Family | 12.0 Checking in |
| | 12.1 Friends and Family |
| | 12.2 How to Get the Support You Need |
| | 12.3 Breaking Unhelpful Food Rules |
| | 12.4 SWiM Practice: Rule Breaking and Being Assertive |
| | 12.5 Going Forward – Maintaining Motivation |

TABLE 1: SWiM Intervention Outline and Content

Web Platform

On the SWiM web platform, intervention content is divided into SWiM sessions, which are each divided into activities. Progress through the sessions is presented as a ‘journey’ using a map-like graphic. Star icons “light up” when activities/sessions are completed (figure.2). As participants complete core skills exercises, these are stored in “SWiM Aids” where they can be accessed without revisiting specific sessions. The web platform is designed to allow participants to revisit past sessions and skills, and it is intended that future roll out would include indefinite access to the website.

Figure 2: Screenshot of participant 'journey' page of SWiM website

The web platform includes a weight tracker, which tracks weight over time, displayed in a visual graphic display. The weight tracker generates a line graph that automatically updates as data is inputted by the participant. As part of the first session, participants are asked to enter their current weight. The weight tracker automatically sets a weight maintenance target range with a boundary of +/-3kg that they are encouraged to stick within. This boundary can be adjusted if required as weight changes over time. Each session starts with a reflection on the previous session and SWiM practice and entry of weight data into the tracker.

5.2 Control Intervention

Participants who are randomised to the control arm will receive standard advice from the European Association for the Study of Obesity (EASO) on diet, physical activity and mood during the COVID 19 pandemic.(6) They will also be wait-listed to receive access to the SWiM website after the study ends.

6. OUTCOMES AND MEASURES

6.1 Primary Outcome

Self-reported weight at 4 months.

6.2 Secondary Outcomes

Patient Health Questionnaire 8-item (PHQ-8) (7,8)

Generalized Anxiety Disorder 7-item (GAD-7) scale(9)

Perceived Stress Scale (PSS-4)

Acceptance and Action Questionnaire Weight Related (Revised) (AAQW-R) (10)

Three-Factor Eating Questionnaire (TFEQ-R21) (11)

International Physical Activity Questionnaire (IPAQ) (12)

Health related quality of life and wellbeing (EQ-5D-L ; ICECAP-A) (13)(14)

Website Usage (data analytics)

They will also complete bespoke questionnaires on demographics and intervention engagement (adapted from Perski et al., 2020)(15)

7. MEASUREMENTS AND DATA COLLECTION

7.1 Visit Schedule

Participants will complete online assessments at 0,4 and 12 months. Details of which measures will be taken at each time point are summarised in Table 4. Participants will be given an honorarium for completing (£10 for baseline and £20 for the 4 and 12 month visit). Honoraria for assessment completion are not dependent on intervention engagement/completion.

TABLE 4: Schedule of Enrolment, Interventions, and Assessments

| | STUDY PERIOD | | | |
|------------------|-----------------|----------|-----------|-----------|
| | Enrolment | Baseline | Follow Up | |
| TIMEPOINT** | -t ₁ | 0 | 4 months | 12 months |
| ENROLMENT: | | | | |
| Online screening | X | | | |

| | | | | |
|--------------------------------------|--|--|---|---|
| Informed consent | | X | | |
| Randomisation | | X | | |
| INTERVENTIONS: | | | | |
| Supporting Weight Maintenance (SWiM) | |  | | |
| Standard Advice | | X | | |
| ASSESSMENTS: | | | | |
| Height | | X | | |
| Weight | | X | X | X |
| Demographics | | X | | |
| Eating Behaviour | | X | X | X |
| Physical Activity | | X | X | X |
| Quality of Life /Wellbeing | | X | X | X |
| Intervention Engagement | | | X | X |

7.2 Outcome Assessments

All outcomes will be assessed via online self-report questionnaires. Participants will be asked to weigh themselves on the day that they complete the outcome assessment so that they can report a self-measured weight. At 12 months, intervention and control participants will complete the intervention engagement questionnaire, since control participants received access to the SWiM website after the 4-month follow-up. This will allow us to control for intervention engagement in analyses, and to compare intervention experiences between intervention participants who received the website in conjunction with support by a coach, and control participants who received only the website without coach support.

Participants will complete a demographics questionnaire at baseline based on Progress-Plus(16) factors.

The study coordination team will send email/phone reminders to participants if a questionnaire has not been completed after 7 days.

7.3 Website analytics

Engagement and intervention usage will be assessed through website analytics. Reports on web-traffic, frequency and duration of visits will be available via secure download directly from the SWiM online platform. Access will be limited to authorised members of the research team.

8. STATISTICS AND QUANTITATIVE DATA ANALYSIS

8.1 Statistical analysis

A detailed statistical analysis plan will be developed and signed off by the Trial Steering Committee (TSC) prior to analysis. Participants will be analysed in the group to which they were randomised, based on the intention-to-treat principle. The primary analysis will estimate the baseline-adjusted difference between intervention groups in change in weight from baseline to 4 months, using a linear regression model including randomisation group, baseline weight, and the randomisation stratifiers (sex, BMI classification). Participants with missing values of weight at 4 months will be excluded (ie, a complete-case analysis which assumes outcome data are missing at random conditional on covariates in the model). If there are >5% of participants with missing values of weight, a sensitivity analysis will be performed using multiple imputation by chained equations – this makes the missing at random assumption but provides increased precision compared with a complete-case analysis. Linear regression will be used to estimate the baseline-adjusted difference between intervention groups in change in weight from baseline to 12 months and 4 months to 12 months. Since the control group was waitlisted and therefore received access to the SWiM website after the 4-month follow-up, analyses at 12 months will need to account for intervention usage in the control group. Regression models for the 12-month follow-up will therefore include intervention engagement (as measured using the intervention engagement questionnaire and/or website analytics) as a covariate. Full details of this analysis will be provided in the statistical analysis plan. Continuous secondary outcomes will be analysed using the same method.

8.2 Sample size calculation

Based on previous trials of weight gain prevention over similar periods, we designed the study to have 90% power to detect a difference between randomised groups in mean change in body weight from baseline to 4 months of 1kg as significant at the 5% level. Based on our previous studies in similar populations, we assumed a SD of 6kg for weight and a correlation between repeated measures of 0.9. Allowing for a 20% drop out, 360 participants (180 per group) would be required.

8.3 Cost-effectiveness analysis

A cost-effectiveness analysis (CEA) will be undertaken, comparing the incremental costs and effects of the SWiM programme (i.e. acceptance-based weight maintenance) versus standard care.

The outcomes used in the cost-effectiveness analysis will be the change in weight over time and the health-related quality of life (HRQOL), which will be expressed in Quality Adjusted Life Years (QALYs). Although the current value set for the 5 levels version of the EuroQol EQ-5D questionnaire (EQ-5D-5L) suffer from low quality and reliability issues, we anticipate that these problems will be solved by the time the analysis will be performed. (17) In the absence of high-quality and reliable value set for the EQ-5D-5L, the analyses will be conducted using the cross-walk algorithm developed by van Hout et al as conform with the NICE position statement. (17,18)

Missing data in outcomes is anticipated, and it will be handled using multiple imputation methods.

The imputed mean cost and mean effectiveness in each arm will be used to obtain an incremental cost-effectiveness ratio (ICER), which is calculated by dividing the mean cost difference by the mean effectiveness difference. These mean differences will be ascertained by using regression methods and will be adjusted by the prespecified subgroups accordingly to the statistical analysis plan.

Additionally, these regressions will be adjusted by the HRQOL, costs and any other unbalanced variable observed at randomisation. The uncertainty around the incremental cost and incremental effectiveness estimates will be calculated using non-parametric methods and presented as cost-effectiveness probabilities. A non-parametric bootstrapping will simulate an appropriate number of pairs of mean cost and effectiveness differences, which will be plotted on the cost-effectiveness plane. Estimating the proportion of the bootstrapped cost and effectiveness pairs with corresponding ICERs below the cost-effectiveness threshold will allow estimating the cost-effectiveness probability. Although NICE has identified a range of acceptable ICERs for an additional cost per additional QALYs (i.e. NICE thresholds: £20-30,000 per QALY), a similar threshold for bodyweight loss measures is not available yet. Therefore, the cost-effectiveness probabilities will be computed by varying the maximum acceptable ICER and each time re-calculating the proportion of plotted points with ICERs below this figure. The so obtained probabilities will enable the construction of the cost-effectiveness acceptability curve. Besides the ICER, we will present the results of the analysis using quality of life data by calculating the net monetary benefits (NMB) of each intervention. NMB will be computed by using the NICE cost-effectiveness thresholds to transform the health benefits in their health care costs equivalent. Therefore, the costs observed during the study will be subtracted to these monetary estimates of the health benefits to obtain the

respective NMB for each arm. The intervention with the highest NMB will be considered cost-effective.

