# 1 Introduction

### 1.1 Trial background and rationale

The social distancing and isolation measures imposed during the COVID-19 pandemic beginning March 2020, including the closure or reduced operating of some weight management programmes and services, mean that adults with overweight and obesity in the UK are at increasing vulnerability to weight gain, and associated negative impacts on physical health and mental wellbeing. There is good evidence that interventions based on acceptance and commitment therapy (ACT) are effective for weight management and may improve mental wellbeing and psychological determinants of weight control.(4) However, acceptance-based programmes are usually psychologist-led and the cost and scarcity of psychologists specialising in obesity mean it is not possible to support everyone who would benefit from this type of intervention.

We developed a supported self-help intervention (SWiM-C; Supporting Weight Management during COVID 19) that aims to help adults with overweight and obesity to manage their weight and eating behaviour, be more physically active, and protect their emotional wellbeing during the COVID pandemic. The 12-week intervention is based on ACT, targets known psychological determinants of weight management and is delivered via an online platform with remote support from a guide or coach.

If the SWiM-C intervention proves to be effective it could be rolled out on a larger scale to support people in situations involving high levels of stress, reduced access to resources, and/or low levels of mobility.

We previously evaluated the effect of SWiM-C on bodyweight in adults with overweight and obesity at 4 months post intervention compared to standard advice (written materials giving advice on diet, physical activity and mental health during the COVID-19 pandemic). The data were compatible with no effect of the intervention on bodyweight, physical activity, mental health, or emotional eating. The intervention improved psychological determinants known to lead to successful weight management in the longer term (uncontrolled eating, cognitive restraint, and experiential avoidance) and had a protective effect on wellbeing.

The current study compares the effectiveness of SWiM-C with standard advice at 12 months post intervention.

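### The cost-effectiveness probability and acceptability curve count bootstrap pairs with an ICER below the threshold, a rule that gives the wrong answer whenever the incremental effect is negative

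*Protocol*

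**What the plan says.** Protocol section 8.3 defines the ICER as a signed ratio, "which is calculated by dividing the mean cost difference by the mean effectiveness difference". Bootstrapping then produces pairs of mean cost and mean effectiveness differences, "which will be plotted on the cost-effectiveness plane". The cost-effectiveness probability is the "proportion of the bootstrapped cost and effectiveness pairs with corresponding ICERs below the cost-effectiveness threshold". The acceptability curve comes from "varying the maximum acceptable ICER and each time re-calculating the proportion of plotted points with ICERs below this figure".

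For QALYs the section cites "NICE thresholds: £20-30,000 per QALY". For weight it says that "a similar threshold for bodyweight loss measures is not available yet", so the threshold is varied.

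No sentence restricts the count by quadrant, sets dominated pairs aside, or reverses the inequality when the effect difference is negative. The section also plans NMB for each arm, for the quality-of-life data only, and calls the arm with the higher NMB cost-effective. NMB is an additional result; it defines neither the probability nor the curve. The SAP has no economic section that changes any of this.

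**The concern.** Comparing an ICER with a threshold is a valid decision rule only when the incremental effect is positive. A negative ICER is ambiguous: it arises both when SWiM is cheaper and better and when it is dearer and worse. The written count puts both in SWiM's favour.

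At stake are the reported probability of cost-effectiveness and the whole acceptability curve, for both outcomes. For QALYs, the probability could point one way and the plan's own NMB verdict the other. For weight, the curve is the only stated basis for judging cost-effectiveness under uncertainty.

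The documents give some reason to expect worse-effect pairs for weight. SAP section 1.1 says of the 4-month results: "The data were compatible with no effect of the intervention on bodyweight, physical activity, mental health, or emotional eating".

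**Working it through.** The plan states no cost-effectiveness figure to reproduce, so the check is of the rule itself and then of its possible size.

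**Algebra.** Let dC and dE be the cost and effect differences (SWiM minus control, effect coded so that higher is better) and λ the threshold. Incremental net benefit is λ × dE − dC, and SWiM is acceptable when it is above zero.

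- If dE > 0: dC/dE < λ is the same as λ × dE − dC > 0. The written rule is right.
- If dE < 0: multiplying by dE reverses the inequality, so dC/dE < λ is the same as λ × dE − dC < 0. The written rule is wrong for every such pair.

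**Example pairs** (net benefit at £20,000 / £30,000 per QALY):

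| Pair | ICER | Counted as cost-effective by the written rule? | Net benefit |
|---|---|---|---|
| £100 dearer, 0.01 QALY gained | £10,000 | yes | +£100 / +£200 |
| £100 dearer, 0.01 QALY lost | −£10,000 | yes | −£300 / −£400 |
| £100 cheaper, 0.01 QALY lost | £10,000 | yes | −£100 / −£200 |
| £500 cheaper, 0.01 QALY lost | £50,000 | no | +£300 / +£200 |

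The last three rows are all misclassified.

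**Size.** The documents give no mean or spread for costs, QALYs or the weight difference, and no value per kg. All inputs below are assumptions: dC has mean £60 and SE £30; the QALY SE is 0.01; the weight SE is 0.5 kg; λ is £20,000 per QALY or £100 per kg; cost and effect are independent normals. The written rule was evaluated by simulation (at least 1,000,000 pairs per scenario). The net-benefit probability also has a closed form, Φ[(λ × mean dE − mean dC) / √(λ² × SE(dE)² + SE(dC)²)]. At zero QALY effect this is Φ(−60 / √(200² + 30²)) = Φ(−0.297) = 38%.

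| Assumed mean effect | Written rule | Net-benefit rule |
|---|---|---|
| QALY −0.005 | 91% | 21% |
| QALY 0 | 88% | 38% |
| QALY +0.01 | 91% | 76% |
| QALY +0.02 | 98% | 95% |
| Weight −0.5 kg (worse) | 87% | 3% |
| Weight 0 kg | 65% | 15% |
| Weight +0.5 kg (benefit) | 59% | 43% |
| Weight +1 kg (benefit) | 78% | 75% |

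The written QALY probability hardly moves between slight harm and moderate benefit. Nor does the written weight probability rise steadily with benefit: it falls from 87% to 59% before rising.

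The gap equals the share of worse-effect pairs with negative net benefit minus the share of worse-effect pairs with positive net benefit. It cannot exceed P(dE < 0), which is 50% at zero effect and Φ(−0.02/0.01) = Φ(−2) = 2.3% at +0.02 QALY.

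**Other assumed costs**, at zero QALY effect and £20,000: mean £50, SE £50 gives 89% against 41%; mean £100, SE £50 gives 81% against 31%; mean £50, SE £200 gives 75% against 43%.

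**Left end of the curve.** As λ tends to 0 with no effect and cost £60 (SE £30), the written rule tends to 50%. The right value is the probability that SWiM saves money, Φ(−60/30) = Φ(−2), about 2%.

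**The case against.** The wording may be only a loose summary. The pairs are to be plotted on the cost-effectiveness plane, and an experienced analyst could read points with ICERs below a figure as points below the line of slope λ, which is the net-benefit rule. That is possible, but the text does not require it. The ICER is defined as a plain ratio, and the count is stated twice without a quadrant condition.

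The QALY decision rule is already sound. If SWiM costs more and yields fewer QALYs, its NMB is lower and the plan does not call it cost-effective. This stands. A reader might infer that the plan would declare a dominated SWiM cost-effective on QALYs; the NMB rule rules that out. What remains for QALYs is a probability and curve that can disagree with the NMB verdict. For weight there is no NMB rule, although no single accepted threshold, and so no single verdict, is planned there either.

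A reader might also infer that the bootstrap cloud must straddle zero effect at positive cost. The documents do not establish this. The null sentence in SAP section 1.1 concerns 4 months and gives no point estimate. The same paragraph reports a protective effect on wellbeing and improvements in eating-behaviour measures. That does not prove a QALY gain, but a null on weight does not prove a zero QALY effect. A positive incremental cost is likewise an assumption: SWiM has a coach call, a tailored email and a platform, but no cost figures are given and other resource use could offset them.

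Finally, the sign of the weight effect is not stated. If raw weight change were the denominator, the signs would reverse. This does not rescue the rule: at 0 kg it still gives 65% against 15%.

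**Conclusion.** The rule is wrong as written, by algebra and not by assumption: whenever the incremental effect is negative, it classifies the pair the wrong way. How much that matters depends on the share of such pairs, which the documents do not give. Under the assumed inputs the gap runs from 2 to 3 percentage points where benefit is clear to about 50 points at no effect, and to 70 points (QALYs) or 84 points (weight) where the effect is slightly worse.

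The null 4-month weight result makes many worse-effect pairs plausible for weight; it does not show this for QALYs. Nor is the error bound to favour SWiM: if many pairs saved enough to justify a small loss, the rule would leave them out.

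Cost-effectiveness is a secondary objective, and the primary weight analysis, randomisation and data collection are untouched. This is a should-fix.

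**What to change.** In both sentences of Protocol section 8.3, define the probability at threshold λ as the proportion of bootstrap pairs for which incremental net benefit, λ × incremental effect − incremental cost, is above zero. Build the acceptability curve from that proportion over a range of λ, for QALYs and for weight. State that the weight effect is coded as kg of benefit (control weight change minus intervention weight change), so that positive means SWiM is better. This aligns the probability and curve with the NMB rule already in the section.

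The cost is two sentences and one line of analysis code. No new data are needed, and the change can be made at any time before the economic analysis is run.
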